SUBJECT IDENTIFICATION	16
INFORMED CONSENT.....	17
CONFLICT OF INTEREST	17
DATA OWNERSHIP AND MANAGEMENT	18
FORMS AND PROCEDURES FOR COLLECTING DATA AND DATA MANAGING	18
OTHER CONSIDERATIONS	20
STATUS	20
FINANCIAL COMPENSATION FOR PARTICIPANTS	20

PUBLICATION POLICY	20
BIBLIOGRAPHY.....	22

Summary

Title	Fluid challenge in Intensive Care: a worldwide global inception cohort study. The FENICE II study
Investigator sponsor	U.O. ANE1, IRCCS Istituto Clinico Humanitas – Rozzano (Milano) Italy. Principal Investigator: [name]
Study coordinator	[name]
Protocol identifying number	FENICE II
Protocol version date	Version 1.0, 30/06/2023
Background and rationale	Fluids are the first line treatment of critically ill patients with shock, Unfortunately, the modality, the volumes and the target adopted to titrate fluid therapy are not standardised in current clinical practice
Aims	The primary aim of the FENICE II study is to globally describe the modality of fluid administration during the first days of intensive care unit (ICU) admission, and to assess if it may impact on in-hospital mortality. Secondary aims are to describe the modality of fluid challenge administration and to appraise the use of variables and functional hemodynamic tests to guide bolus infusion.
Population	All consecutive adult (≥ 18 years old) patients admitted to ICU and expected to stay at least 48h.
Study design and study duration	Prospective multicentre worldwide study

Introduction

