Research question

What is the modality of fluid administration in ICU patients worldwide and what is the impact of fluid administration on clinical outcomes?

Aims

The primary aim of the FENICE II study is to describe the modality of fluid administration in the acute phase of resuscitation from hemodynamic instability in ICU patients.

As secondary aims, we'll appraise in-hospital, ICU and 30-day mortality and major organ dysfunction. Finally, we'll assess the use of variables (including clinical signs of hypovolemia, and indexes/images obtained from hemodynamic monitoring or echography) and functional hemodynamic tests to guide FC infusion in ICU patients, and the modality of FC administration (i.e. volume, rate, type of fluid), of evaluation of fluid responsiveness at the bedside.

Methods

Enrollment and study period

The phase of centers enrolment will be conducted over a time window of 12 months starting from 1st January 2024.

The phase of patients' enrolment will be conducted over a two-weeks period (14 days), chosen within a time window of 6 months starting from 1st January 2025.

The study period for data collection regarding the modality of fluid administration will consider the first 5 days from ICU admission (ICU days 1-5).

INPUT - Fluid data collection – definitions

Fluid Challenge/Fluid bolus (FC in test)

The FC is defined as the administration of any bolus of fluid (crystalloid or colloid) which is expected to affect pressure/flow/perfusion variables. The FC is expected to be completed within 30 min. Whenever possible, the exact time of fluid infusion will be collected. Considering the observational nature of the study, the indication for FC will be triggered by the decision of the attending ICU physician at the bedside (according to clinical practice of the ICU).

Continuous IV fluid administration (fluid maintenance or any other type of fluids given)

Any form of fluid infusion given for the purpose of optimizing overall fluid balance or to manage electrolytes (i.e. continuous infusion of any type of crystalloids). (*ml*)

Other IV fluids

Any form of fluid infusion received by the patients in the context of the therapy adopted (i.e. drugs solutions, glucose control, parenteral nutrition etc). (*ml*)

Blood products

Administration of red blood cells or fresh frozen plasma. (ml)

Other non IV intake

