- Evolvement of central venous pressure (Time Frame: up to day 5 - highest and lowest value)
- Evolvement of central venous oxygen saturation (Time Frame: up to day 5 - worst value)
- Evolvement of central venous to arterial carbon dioxide difference (Time Frame: up to day 5 - worst value)

Statistical analysis

Data will be described as median and interquartile range (IQR) or number and percentage. Categorical variables were compared using Fisher's exact test and continuous variables using the nonparametric Wilcoxon test, Mann-Whitney test, or Kruskal-Wallis test.

In way to assess volume of fluid received, group-based trajectory modeling (GBTM) will be used to identify clusters of patients with similar patterns of fluid administration profile. GBTM is a semiparametric technique used to identify distinct subgroups of individuals following a similar pattern of changes over time for a given variable [23]. To do so, we will use the R-software “kml” package that implements the k-means algorithm in context of longitudinal data [24]. Briefly, longitudinal change in fluid received each day from day 1 to day 3 will be assessed. In way to avoid misinterpretation of findings due to time dependent competing events such death or ICU discharge, this analysis will be performed on patients alive and still in the ICU at day 3. The optimal number of clusters was evaluated using Calinski & Harabasz criterion [25].

In way to assess impact of fluid administration strategy, factors associated with in-hospital mortality, including identified cluster of fluid administration, will be assessed using mixed logistic regression where in-hospital mortality will be event of interest. Variables of interest will be selected according to their relevance and statistical significance in univariate analysis. We will use conditional stepwise regression with 0.2 as the critical P-value for entry into the model, and 0.1 as the P-value for removal. It will be planned a priori to force identified clusters and relevant variable related to hemodynamic instability in the model. Last, the center effect will be included as a random effect against the intercept. Should a center effect be identified, a secondary analysis in line with centers characteristics will be performed. Interactions and correlations between the explanatory variables will be checked. Continuous variables for which log-linearity will not confirmed, will be transformed into categorical variables according to median or IQR.

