For secondary outcomes, and in particular for day-30 mortality, number of days alive without vasopressors, mechanical ventilation or renal replacement therapy, will be assessed using survival analysis.

All tests will be two-sided, and P-value less than 0.05 will be considered statistically significant. Analyses will be performed using R software version 3.4.4 (<https://www.r-project.org>), including ‘kml’, ‘caret’, ‘lme4’, and ‘lmerTest’ packages.

Sample size

Considering the results of the FENICE study, we plan to enrol 10,000 patients and 15,000 FCs [30 patients / centre (max) and > 300 centres (min)]. The planned number of patients to be enrolled is in line with previous similar large observational trials regarding the use of fluids in ICU patients with the purpose of assessing current clinical practice and potential impact on clinical outcomes.

Data imputation

No data imputation will be performed on main outcome variables. Patients discharge alive from hospital, not admitted in rehabilitation unit or palliative care unit and/or lost of sight will be considered alive and free from organ support until day 30. Missing daily fluid volume will be imputed only if available every other day in which case it will be averaged.

Sensitivity analyses

In way to assess impact of fluid administration strategies, fluid volume considering only high chloride concentration fluids and impact of hypotonic fluids, three dedicated analyses using same methods than main analysis will be performed.

Ethical considerations and personal data protection

Patient protection

The responsible investigator will ensure that this study is conducted in agreement with either the Declaration of Helsinki or the laws and regulations of the country. The protocol has been written, and the study will be conducted according to Guideline for Good Clinical Practice. The protocol and its annexes are subject to review and approval by the competent Independent Ethics Committee(s) (“IEC”).

Subject identification

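### The Data imputation rule counts patients with unobserved day-30 status as alive and free of organ support: an untested best-case imputation of secondary outcomes

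*Protocol*

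**What the plan says.** The Data imputation section opens with "No data imputation will be performed on main outcome variables". The next sentence sets the rule at issue: "Patients discharge alive from hospital, not admitted in rehabilitation unit or palliative care unit and/or lost of sight will be considered alive". Its second half reads in full "and/or lost of sight will be considered alive and free from organ support until day 30", so the assumed status covers organ support as well as survival.

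The protocol never says which outcomes are the main ones. The Summary attaches mortality to the primary aim, "to assess if it may impact on in-hospital mortality". The Aims section places all mortality outcomes lower: "As secondary aims, we'll appraise in-hospital, ICU and 30-day mortality and major organ dysfunction". Under Statistical analysis, factors associated with mortality "will be assessed using mixed logistic regression where in-hospital mortality will be event of interest". Survival analysis is planned "For secondary outcomes, and in particular for day-30 mortality, number of days alive without vasopressors, mechanical ventilation or renal replacement therapy".

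The Sensitivity analyses section lists three analyses. They concern fluid strategy, high-chloride fluids and hypotonic fluids. None changes the handling of patients whose day-30 status is unknown.

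**The concern.** Where nobody checked a patient's status at day 30, the rule fills in the best possible answer. A death at home after discharge that the centre did not learn of becomes a survivor, with support-free days credited to the end of the window. The error runs in one direction only.

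Two outcomes are exposed: 30-day mortality, and the count of days alive without organ support to day 28. With more than 300 centres planned worldwide, completeness of follow-up after discharge could well vary. If it does, and if fluid practice varies along with it, comparisons of 30-day mortality between centres or fluid clusters would partly reflect follow-up rather than outcome.

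The sentence is also hard to parse. The and/or can be read in three ways:

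- it covers anyone lost;
- it covers only patients discharged alive and then lost;
- if the word not governs the whole list, it leaves lost patients out of the rule.

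A rule that decides who is counted as alive should have one reading.

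**Working it through.** The plan gives no loss rate, expected 30-day mortality or post-discharge death risk, so there is no figure of its own to reproduce. The direction can be derived. The size can only be shown as scenarios.

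**Inputs**

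- h, in-hospital mortality: 14% and 42%. These are the averaged mortalities of two trials cited in the Introduction, used only as an illustrative range. They are not estimates for this cohort.
- L, share of patients discharged alive whose day-30 status is unknown: 2% to 20% (assumption).
- q, risk of death between discharge and day 30: 2% to 10% (assumption), taken as equal in lost and followed patients.
- Planned size: 10,000 patients, at most 30 per centre (Sample size).

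**Step 1: direction.** True 30-day mortality is h + (1-h)q. Under the rule it is h + (1-h)(1-L)q. The error is -(1-h)Lq, which is never positive.

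**Step 2: size.**

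| h | L | q | True | Under the rule | Shortfall (points) | Deaths missed per 10,000 |
|---|---|---|---|---|---|---|
| 42% | 2% | 2% | 43.16% | 43.14% | 0.02 | 2 |
| 14% | 10% | 5% | 18.30% | 17.87% | 0.43 | 43 |
| 42% | 20% | 10% | 47.80% | 46.64% | 1.16 | 116 |
| 14% | 20% | 10% | 22.60% | 20.88% | 1.72 | 172 |

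**Step 3: between centres.** For two centres with the same h and q, the spurious gap is (1-h)q(L1-L2).

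- Loss of 20% against none: from 0.58 × 0.02 × 0.20 = 0.23 points to 0.86 × 0.10 × 0.20 = 1.72 points (odds ratios 0.99 to 0.90). In a centre with 30 patients, 1.72 points is 30 × 0.0172 = 0.5 deaths.
- No post-discharge follow-up at all against complete follow-up: from 0.58 × 0.02 = 1.16 points to 0.86 × 0.10 = 8.6 points (odds ratios 0.95 to 0.56).
- Equal loss: zero.

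**Step 4: would censoring at last contact repair it?** Often the last contact is the discharge itself. As an illustration, assume constant hazards of in-hospital death 0.014 and discharge 0.086 per day, 5% of discharged patients dying by day 30, and no follow-up after discharge.

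- In-hospital death by day 30: (0.014/0.100) × (1 - exp(-3)) = 13.3%. This is also the estimate under the rule.
- Discharged by day 30: 0.86 × 0.950 = 81.7%. Of these, 5% die, adding 4.1 points.
- True 30-day mortality: 13.3% + 4.1% = 17.4%.
- Censoring at discharge: 1 - exp(-0.014 × 30) = 1 - exp(-0.42) = 34%.

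The rule errs by about -4 points and censoring by about +17. Discharge is informative, because patients who leave are at lower risk than those who stay.

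**Step 5: width of a worst-case bound.** If every lost patient is counted as dead, the estimate rises above the rule's value by (1-h)L: from 0.58 × 0.02 = 1.16 points to 0.86 × 0.20 = 17.2 points. With high loss this bound says little by itself, so intermediate, plausible risks are needed as well.

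**The case against.** The strongest defence is that this is a reasonable convention for secondary outcomes. The no-imputation sentence covers only the main outcome variables. In-hospital mortality is known for anyone discharged alive, so the rule leaves it unchanged. The carve-out for rehabilitation and palliative care removes groups in whom death after discharge is most plausible. Vasopressor-free and renal-replacement-free days are defined within the ICU stay, so status after discharge hardly touches them. Step 4 shows that the obvious alternative can be further from the truth. Finally, loss tables and bounds are usual SAP content, and the SAP is not at hand.

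Most of this stands, and it rules out stronger readings that a reader might infer:

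- **That the two sentences contradict each other outright.** They do so only if the undefined main outcome variables include 30-day mortality. The Aims and Endpoints sections list it as secondary, although the Statistical analysis section singles it out.
- **That the rule certainly reaches everyone lost.** The wording allows this but does not settle it.
- **That mortality is understated differentially by centre.** The documents give no follow-up rate by centre, and with equal loss the gap is zero. It is a risk.
- **That every early discharge has unknown status**, which would give much larger errors. Nothing in the protocol says that discharged patients will not be followed.
- **That lost patients gain maximal support-free time.** Support days observed in hospital still count. Only the days after discharge are filled in.

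The defence does not remove the core of the point. The protocol itself fixes the best-case value, so this is not a detail left for later. The rule is one-sided, and no listed sensitivity analysis tests it.

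**Conclusion.** The point holds for secondary outcomes. Where day-30 status is unobserved, the rule can only lower 30-day mortality and raise days alive without organ support. The documents do not give the size. With 2-20% of discharged patients lost, 2-10% dying after discharge and in-hospital mortality of 14-42%, the understatement is about 0.02 to 1.7 points, or 2 to 172 deaths per 10,000. Higher risk among lost patients than assumed would increase it. Distortion between centres or fluid clusters is possible if loss differs between them, but it is not shown.

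The in-hospital mortality regression and the description of fluid administration are unaffected. The no-imputation sentence and the rule need reconciling because the scope of the first and the coverage of the second are both unclear.

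**What to change.** 1. Define the main outcome variables, so that the no-imputation sentence has a clear scope.
2. Reword the rule so that it has one reading. Use observed day-30 status, including known organ support, wherever it is available.
3. Limit the assumption to patients discharged alive whose later status is unknown, and label the result a lower bound for 30-day mortality. Treat patients lost in other ways as missing.
4. Record the last date known alive, and report the number with unknown day-30 status by centre and by fluid cluster.
5. Add sensitivity analyses for 30-day mortality and support-free days under the worst case and under plausible post-discharge death risks.
6. Do not make censoring at discharge the main estimate. Show it at most as an upper bound, which it is only as long as discharged patients are at lower risk than those still in hospital.

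The cost is one extra date on the case report form, best captured prospectively, a few sentences of text and a little more analysis. The day-30 results will show more uncertainty.

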Any other form of non-IV intake received by the patients in the context of the therapy adopted (i.e. nutrition, solutions given for oral therapy).

OUTPUT

- *Urine output (ml)*
- *Blood loss (ml)*
- *Drainages (thorax, abdomen) (ml)*
- *Leak from other sites (estimation) (ml)*

Daily fluid balance

- *24 h fluid balance of the first 5 days (ml)*

Inclusion / Exclusion criteria

Inclusion Criteria:

- All consecutive adult (≥ 18 years old) patients admitted to ICU and expected to stay at least 48h.

Exclusion criteria:

- Planned admission after surgery for overnight ICU stay.
- Refusal of consent
- Moribund patients (i.e. expected survival < 24 h)

Endpoints

Primary aim: the primary aim is to describe the modality of fluid administration during the first 5 days of ICU stay considering 1) the overall fluid balance; 2) the characteristics of the fluids given; 3) the modality of fluid administration (i.e. FC and not FC).

Secondary aims:

- The secondary aim is to explore any association between fluid administration characteristics and clinical outcomes (see further)
- To evaluate factors potentially associated with the respective proportion of the different modalities of fluid administration
- To characterize FC administration modality in a large cohort of ICU patients.

Secondary clinical outcomes

- In-hospital mortality
- ICU mortality
- 30-days mortality
- Alive without any organ support (the number of calendar days between inclusion and 28 days that the patient is alive and with no requirement of cardiovascular, respiratory and renal support. Patients who die during ICU stay will have zero days counted for this variable, irrespective of vital support status)
- Organ dysfunction:
 - Lung
 - Time to cessation of mechanical ventilation during ICU stay [The number of calendar days between intubation / start of mechanical ventilation and extubation / liberation from mechanical ventilation, including non-invasive mechanical ventilation (maintained for at least 48 hours)].
 - Mechanical ventilation support-free days free days from day 1 to day 28. Cessation of mechanical ventilation support implies its complete interruption for at least 24 consecutive hours)

- Ventilation Associated Pneumonia (VAP) cumulative incidence (number of VAP per patient) and rate (number of VAP per 1000 days of MV) [22].
- Heart

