 - Time to cessation of vasopressor support during ICU stay (The number of hours between enrollment and complete stopping of vasopressor support (defined as its complete interruption for at least 24 consecutive hours).
 - Vasopressor support-free days during ICU stay from day 1 to day 28. Cessation of vasopressor support implies its complete interruption for at least 24 consecutive hours)
 - Inotropes-support free days
- Kidney
 - Time to cessation of Renal Replacement during ICU stay [The number of calendar days between start of renal replacement therapy and complete liberation from renal replacement therapy (at least 48 hours for continuous replacement modalities and 5 days for intermittent ones).
 - Renal Replacement support-free days during ICU stay from day 1 to day 28. Cessation of Renal Replacement support implies its complete interruption at least 48 hours for continuous replacement modalities and 5 days for intermittent ones)
 - Variation of creatinine-based KDIGO stage (Time Frame: 7 days after ICU admission). Renal function assessed according to KDIGO staging system from randomization through day 7 to assess for “de novo” or “worsening” acute kidney injury. Patients under chronic renal replacement therapy will not meet this end-point
- Variation in Sequential Organ Failure Assessment (SOFA) score (Time Frame: 7 days)

Sequential Organ Failure Assessment (SOFA) score calculated upon the maximum values observed on the day of enrollment and then, at days 2, 3, 4, 5 and 7 (or until patient discharge or death, if this happened before day-7), using clinically available data. If an individual organ dysfunction value is not available (i.e., cardiovascular, respiratory, renal, etc.), it will be assumed to be zero unless previous value was abnormal (in which case it would be considered the same organ score). Neurological score under sedation/invasive mechanical ventilation will be computed as that observed just before sedation/intubation.

Secondary functional outcomes

- Volume of resuscitation fluids (Time Frame: up to day 5). The volume of fluids administered with resuscitative intention up to 5 days from inclusion
 - Type of fluids
 - Modality of fluid administration
- Net fluid balance (Time Frame: up to day 5).
- Evolution of Capillary Refill Time (CRT) (Time Frame: up to day 5 - worst value)
- Evolution of Lactate levels (Time Frame: up to day 5 - worst value)

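### The discharge rule sets no condition on support status, so a survivor who leaves hospital on dialysis or ventilation is credited with support-free days to day 28

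*Protocol*

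**What the plan says.** The rule is in the Protocol, Data imputation. It covers "Patients discharge alive from hospital, not admitted in rehabilitation unit or palliative care unit and/or lost of sight", and these patients "will be considered alive and free from organ support until day 30". The only exception is by destination. Support status at discharge is not mentioned, and the and/or wording makes discharge alive sufficient without loss to follow-up.

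The outcomes it feeds are defined under Secondary clinical outcomes:

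- **Days alive without organ support.** Calendar days from inclusion to day 28 on which the patient is "alive and with no requirement of cardiovascular, respiratory and renal support". The count is not limited to the ICU stay.
- **Ventilation-free days, day 1 to 28.** "Cessation of mechanical ventilation support implies its complete interruption for at least 24 consecutive hours".
- **Renal replacement-free days.** Worded as "Renal Replacement support-free days during ICU stay from day 1 to day 28", with the criterion "Cessation of Renal Replacement support implies its complete interruption at least 48 hours for continuous replacement modalities and 5 days for intermittent ones".

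Two further statements in the same section bear on the point. A SOFA component that is unavailable is scored zero unless the last value was abnormal, in which case that value is kept. In the KDIGO item, "Patients under chronic renal replacement therapy will not meet this end-point", so the protocol expects to enrol patients on chronic dialysis. The exclusion criteria do not remove them.

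**The concern.** The outcome definitions ask whether support was still needed, and the discharge rule asks only where the patient went. A survivor who goes home on dialysis, or moves to another hospital or a long-term facility while still ventilated, needs support under the definitions but is free of it under the rule. The values assigned to such patients are wrong in one direction only: each gains days, and more of them with earlier discharge. Leaving hospital dependent on organ support is an unfavourable result that a study of fluid administration would want these outcomes to register. Here it is scored as recovery.

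**Working it through.** The protocol states no figure tied to this rule, so there is nothing to reproduce. The check compares the two scorings for one patient and then asks what can be said about the cohort.

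**Inputs from the protocol.** The window ends on day 28 (composite and ventilation-free days). The discharge rule runs to day 30, so it covers all the remaining days of that window. Cessation needs 24 hours off ventilation, 48 hours off continuous renal replacement, or 5 days off intermittent renal replacement.

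**Assumptions (not in the protocol).** Renal replacement starts on day 3. The patient goes home on thrice-weekly dialysis on day 10, 12 or 15. The day of discharge counts as supported. Gaps between sessions are shorter than 5 days, so cessation is never met. The composite has no cessation threshold of its own; I take the need for renal support to continue between sessions, as the 5-day criterion implies. No other organ support is in use on days 1 and 2 or after discharge.

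**Formulas.**
- Days under the outcome definitions = start day − 1 = 3 − 1 = 2.
- Days added by the discharge rule = 28 − discharge day.

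| Discharge day | By the definitions | Added by the rule | By the rule |
|---|---|---|---|
| 10 | 2 | 28 − 10 = 18 | 20 |
| 12 | 2 | 28 − 12 = 16 | 18 |
| 15 | 2 | 28 − 15 = 13 | 15 |

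The excess does not depend on the start day. It is the same for ventilation-free days in a patient discharged while still ventilated.

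**Chronic dialysis.** For a patient already on dialysis at admission, the composite is 0 days by the definitions and 28 minus the discharge day by the rule. This case needs no new dialysis dependence.

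**Comparison with the SOFA rule.** Where an organ score is unavailable and the last one was abnormal, the protocol carries the abnormal value forward. Where organ support after discharge is unavailable and the last status was supported, the discharge rule resets it to unsupported. The same kind of gap is filled in opposite directions.

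**Cohort level.** Shift in the mean = affected share × excess days. The protocol gives no share. For assumed shares of 0.5% to 5% and an excess of 7 to 18 days (discharge on day 21 to day 10), the shift runs from 0.005 × 7 = 0.035 to 0.05 × 18 = 0.9 day. This range shows how little can be fixed from the document. It is not an estimate of bias.

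**The case against.** **The rule may only fill gaps.** It stands under Data imputation, follows the sentence "No data imputation will be performed on main outcome variables", and names patients lost to follow-up. A reader might infer that the protocol overwrites a recorded status of ongoing dialysis. The text does not say so, and that reading is not adopted here. The objection does not remove the problem: even as a gap-filler, the rule sets a patient last seen on dialysis to support-free.

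**Renal replacement-free days may be out of reach.** A reader might apply the 16-day excess directly to that outcome. Its wording refers to the ICU stay, and days after hospital discharge lie outside that stay. The same phrase also gives a day 1 to 28 window, so the scope is unclear. The objection stands: the firm conflict is with the composite and with ventilation-free days.

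**The size of any group bias is unknown.** With assumed shares of 4% against 1%, or 6% against 2%, discharged on dialysis, the difference in means would be 0.03 × 16 = 0.48 or 0.04 × 16 = 0.64 day. A reader might take these as bias that the rule hides. The shares have no basis in the document. The Statistical analysis section also plans medians, rank tests and survival analysis, so a difference in means is not the planned measure. This objection stands in full.

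**Kidney harm is followed elsewhere.** KDIGO change to day 7 and time to cessation of renal replacement during the ICU stay need no days after discharge. This stands: the rule does not make kidney harm undetectable.

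**The SAP or e-CRF may settle it.** Neither was available for this point. Precedence of observed over assumed status could be stated in the SAP, and a field for support at discharge may exist. But the protocol has already fixed a rule without a condition, so its text needs correcting either way.

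**Conclusion.** The point holds for secondary outcomes. As written, the discharge rule gives values that conflict with the protocol's own definitions for days alive without organ support and for ventilation-free days. The error per affected patient is 28 minus the discharge day, always in the favourable direction. That size rests on support continuing from discharge to day 28 and on discharge to somewhere other than rehabilitation or palliative care. The exception for those destinations removes some dependent survivors, but not those who go home or to another hospital. Because chronic dialysis patients are eligible, the case can be expected to arise.

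Renal replacement-free days are affected only if days after the ICU stay are counted. The descriptive primary aim and the in-hospital mortality model do not use the rule. The document does not support a figure for the number of affected patients or for bias between fluid groups, nor a claim that recorded data are deliberately replaced.

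**What to change.** In Data imputation, limit the assumption to patients who had met the protocol's cessation criteria before discharge and whose later status is unobserved. State that recorded support status prevails. For patients still supported at discharge, carry that status forward to day 28 unless cessation is documented; this matches the SOFA convention. In the Kidney item, say whether renal replacement-free days include days after the ICU stay.

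Record support status at hospital discharge in the e-CRF, if it is not already collected.

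The cost is a short qualification in one section, a clarification in another, and at most one field taken from the chart. The downside is that patients who stop support soon after discharge, without this being documented, lose a few support-free days.
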